#### 9.4.1.4. PK Analysis Set

The Pharmacokinetic Analysis Set (PAS) will include all subjects who receive at least one dose of DS-1594b and have at least one evaluable PK sample. The PAS will be used for summaries of PK data as well as for listing of derived PK parameters. The definition of PK evaluability for the DDI sub-study and food effect sub-study are described in Section 3.2.3.3 and Section 3.2.4.3, respectively.

#### 9.4.2. Analysis Convention

##### General rule

Baseline is defined as the last non-missing value before the first dosing of study drug. The day of treatment would be considered as Day 1. Both the scheduled and unscheduled assessments will be used in the scope of analysis. For Phase 1, results will be presented by dose level and in total excluding subjects enrolled in the two sub-studies. The results from the DDI sub-study and food effect sub-study will be presented separately. For Phase 2, results will be presented by Cohort and in total, unless otherwise stated.

##### Visit window

For the summary at scheduled post-treatment visits, a continuous visit window would be used. For example, for visit scheduled at Day X, the visit window starts on day prior to  $X_L = [(X+Y)/2]_+$  and ends on Day  $X_U = [(X+Z)/2]_+$  where Y is the scheduled day of prior visit, Z is the scheduled day of next visit and  $[x]_+$  is the least integer greater than or equal to x. The visit window for a given scheduled post-treatment visit can be different for different assessments depending on schedule assessments as not all the assessments are planned at each visit.

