**Table 21: ECG Collection During Phase 2 Dose Expansion**

Cycle	Day	Time	Comment
Screening	-28 to -1	Anytime	
1	1	Pre-dose/0h a	
1	1	Post-dose 2h	
1	1	Post-dose 4h	
1	8	Pre-dose/0h a	
1	8	Post-dose 2h	
1	8	Post-dose 4h	
1	15	Pre-dose/0h a	
1	15	Between 2-4 hours post-dose	
2-6	1	Pre-dose/0h a	
During treatment after Cycle 6	Any day b	Anytime	
End of Treatment	--	--	

All measurement times are relative to dose of DS-1594b unless otherwise specified.

a Pre-dose assessment should be taken prior to the next administration of DS-1594b and within 15 minutes prior to PK collection.

b ECG should be performed only if clinically indicated.

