##### Multiple assessments

For multiple assessments within a particular visit window the assessment closest to the scheduled day of visit would be used. If there are multiple equi-distant assessments within a visit window, the assessment collected after the scheduled day of visit would be used. If there are multiple assessments, on a particular day, the worst value would be used.

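### As written, the visit-window rule makes every pair of adjacent windows share two days, so when a visit is missed one assessment can be summarised at two visits

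*Combined protocol and SAP*

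**What the plan says.** Section 9.4.2 (Visit window) states that for summaries at scheduled post-treatment visits "a continuous visit window would be used". With Y, X and Z as the scheduled days of the previous, current and next visit, it defines X_L as the midpoint of X and Y and X_U as the midpoint of X and Z. Both are rounded up, since the bracket notation "is the least integer greater than or equal to x". For the visit on Day X, "the visit window starts on day prior to" X_L, and it ends on Day X_U.

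Two neighbouring rules bear on this. Under General rule, "Both the scheduled and unscheduled assessments will be used in the scope of analysis". Under Multiple assessments, "For multiple assessments within a particular visit window the assessment closest to the scheduled day of visit would be used". A value after the scheduled day wins a tie in distance, and the worst value is taken when there are several on one day.

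**The concern.** Continuous windows should cover every day once, so that each assessment belongs to one visit. Here the phrase that moves a boundary back by a day is attached to the start of the window. The earlier window already runs up to and including the shared midpoint, and the later window opens the day before that midpoint. No rule in Section 9.4.2 says which visit owns an assessment that falls in both.

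The by-visit tables of laboratory results, vital signs and ECG parameters (Sections 9.4.7.2.3, 9.4.7.3 and 9.4.7.4) are at stake. A value used twice makes a missed visit look observed and pulls two adjacent visit summaries together. Two programmers could also resolve the overlap differently and get different tables from the same data. ECGs deserve most care, because QTc prolongation is an adverse event of special interest in this trial.

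**Working it through.** **Inputs.** The window rule is in Section 9.4.2. The Phase 2 ECG days are in Table 21: Days 1, 8 and 15 of Cycle 1, then Day 1 of Cycles 2-6. The Phase 1 once-daily ECG days are in Table 20: Days 1, 2, 5, 8, 9, 15 and 21 of Cycle 1, then Day 1 of Cycle 2. With undelayed 28-day cycles, Cycle 2 Day 1 is Day 29. The plan gives no worked windows, so there is no stated figure to reproduce.

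**General result.** Take adjacent visits on Days X and Z and let m = ceil((X+Z)/2).
- The window for X ends on X_U = m.
- For the visit on Z, X_L is also m, so its window starts on m - 1.
- The shared days are m - 1 and m: two days, whatever the spacing and whether X + Z is odd or even.

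**Phase 2 ECG, as written**
- Day 8: start ceil((8+1)/2) - 1 = 5 - 1 = 4; end ceil((8+15)/2) = 12. Window 4-12.
- Day 15: start 12 - 1 = 11; end (15+29)/2 = 22. Window 11-22.
- Shared: Days 11-12.

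**Phase 1 once-daily ECG, as written**
- Day 2: start ceil((2+1)/2) - 1 = 2 - 1 = 1; end ceil((2+5)/2) = 4. Window 1-4, which reaches back to the first dosing day.
- Day 8: start ceil((8+5)/2) - 1 = 7 - 1 = 6; end ceil((8+9)/2) = 9. Window 6-9.
- Day 9: start 9 - 1 = 8; end (9+15)/2 = 12. Window 8-12.
- Days 8 and 9 both lie in both windows.

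**When a value is actually used twice.** It must lie on a shared day and be the closest assessment available for both visits.
- Phase 1 once-daily: a subject has the Day 8 ECG, misses Day 9 and is next seen on Day 15. The Day 8 ECG is closest to Day 8, and it is the only ECG in 8-12. It is summarised at both visits. One missed ECG is enough.
- Phase 2: a subject's only ECG from Day 4 to Day 22 is on Day 11 or 12. It is summarised at both Day 8 and Day 15.

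**Other ways of reading or repairing the rule**

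| Start | End | Shared days | Day 9 window (Phase 1 once-daily) |
|---|---|---|---|
| X_L - 1 | X_U | 2 (as written) | 8-12 |
| X_L | X_U | 1 | 9-12 |
| X_L - 1 | X_U - 1 | 1 | 8-11 |
| X_L + 1 | X_U | 0 | 10-12, excludes Day 9 |
| X_L | X_U - 1 | 0 | 9-11 |

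Dropping the day-before phrase altogether still leaves one shared day. Only the last row removes the overlap and keeps Day 9 in its own window. It does so in general: since Y < X, ceil((X+Y)/2) is at most X, and since Z > X, ceil((X+Z)/2) - 1 is at least X.

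**The case against.** The strongest reply is that this will rarely change a table. The closest-assessment rule already handles most cases: an unscheduled value on Day 11 or 12 enters neither summary when the subject has nearer Day 8 and Day 15 values. Table 33 allows one day either side of Days 8 and 15, so on-schedule visits fall on Days 7-9 and 14-16, outside the shared days. Section 8.3 requires laboratory tests at least three times a week in Cycle 1 and twice a week in Cycles 2 and 3, so a closer laboratory value will usually exist. Wide windows can also fill a missed visit with an off-schedule value without any overlap. Finally, the formula is introduced as an example.

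Most of this stands, and it limits the point. A reader might infer that every value on a shared day is counted twice. The Multiple assessments rule rules that out. A reader might also infer that all filling of missed visits comes from this error. Only the second use of the same value does.

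Two things survive. Where ECG visits are one day apart, the shared days are the scheduled days themselves, so the visit tolerances give no protection and a single missed ECG triggers double use. And although it is offered as an example, the formula is the plan's only definition of the window limits, so programmers will code it.

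**Conclusion.** Wrong as written, and minor. The two-day overlap is exact for every pair of adjacent visits and depends only on reading the start and end days as included in the window, which is what the text says. The Day 29 figure assumes undelayed 28-day cycles; the overlap itself does not.

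The consequence is conditional. A value is used twice only if neither visit has a closer one. The documents give no missed-visit rate, so no frequency can be put on it. The risk is clearest for the Day 8 and Day 9 ECGs under once-daily dosing and weakest for laboratory tests.

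A reader might infer a threat to the trial's conclusions or its QTc safety signal. The documents do not support that. The primary response rate and the DLT decisions do not use these windows. The maximum and minimum post-treatment summaries, the worst-grade laboratory shift tables and the maximum QTc categories draw on all post-treatment values. Only the descriptive by-visit summaries are exposed.

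**What to change.** In Section 9.4.2 (Visit window), move the day-before phrase from the start of the window to its end: the window for Day X starts on Day X_L and ends on the day before X_U. Adjacent windows then meet with no gap and no overlap:
- Phase 2 ECG: Day 8 = 5-11, Day 15 = 12-21.
- Phase 1 once-daily ECG: Day 2 = 2-3, Day 8 = 7-8, Day 9 = 9-11.

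Do not instead keep X_U and start on the day after X_L. That also removes the overlap, but it pushes some visits out of their own windows: Day 2 would become 3-4 and Day 9 would become 10-12, so on-time ECGs would be misassigned.

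The cost is one phrase in the plan, made before the by-visit tables are programmed. It changes no data collection, sample size or decision rule.

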##### Multiple assessments

For multiple assessments within a particular visit window the assessment closest to the scheduled day of visit would be used. If there are multiple equi-distant assessments within a visit window, the assessment collected after the scheduled day of visit would be used. If there are multiple assessments, on a particular day, the worst value would be used.

#### 9.4.3. Analysis of Subject Disposition, Demography and Baseline Characteristics, and Medical History

Subjects disposition (e.g., number of subjects screened, treated, completed study drug, completion of study, reason for discontinuation) will be summarized using counts and percentages. Subject demography and relevant baseline characteristics and medical history will be summarized descriptively for all treated subjects (i.e., the safety analysis set).

#### 9.4.4. Analysis of Exposure of Study Drug

Study treatment exposure and treatment duration will be summarized using descriptive statistics for the Safety Analysis Set. In addition, the total number of cycles initiated will be summarized using descriptive statistics. Number and percentage of subjects with and without dose reductions

or interruptions will also be summarized. In addition, cumulative dose and dose intensity will also be summarized.

The following definitions would be used:

Exposure (in days): last dose date – first dose date + 1

Treatment duration (in days): last dose date – first dose date + 30

Cumulative dose: Total amount dose actually taken

Dose intensity: Cumulative dose/ Exposure

#### **9.4.5. Analysis of Prior and Concomitant Medications**

Prior and concomitant medications will be coded using the World Health Organization drug dictionary (WHO-DD). Concomitant medications will be summarized by ATC2 class and preferred term for the Safety Analysis Set. Prior medications will be summarized for the Safety Analysis Set. Within each level of summarization, a subject will be counted once if he/she takes one or more medications.

Prior medications are defined as those with a start date prior to the date of first dose of study drug. Concomitant medications are defined as those with a start date greater than or equal to the date of first dose of study drug, or with a start date prior to the date of first dose of study drug and a stop date either after the date of first dose of study drug or marked as “ongoing” or “continuing”. Medications taken prior to the first dose of study drug, but with a missing stop date or with a stop date either on or after the date of the first dose of study drug or marked as “ongoing” or “continuing” will also be considered concomitant medications for the summary. Medications started after the 40-day visit or after start of new anticancer therapy are not considered as concomitant medications. A listing of prior and concomitant medications by subject will also be provided.

#### **9.4.6. Efficacy Analyses**

The efficacy analyses will be carried out for both the Efficacy Analysis Set and the Safety Analysis Set. Subjects with prior treatment with other menin inhibitors will be analyzed separately for efficacy.

For the primary efficacy analysis, the primary efficacy outcome (CR + CRh rate for Cohorts A, B, C and CR+CRi rate for Cohort D) will be estimated along with the 95% credible interval for each cohort. If the study cohort is not stopped early, assuming 11 of the 26 subjects achieve the response (CR + CRh for Cohorts A, B, C and CR+CRi for Cohort D), the 95% credible interval for the response rate will be (25%, 61.3%). The same method will be used for other binary efficacy outcomes in Phase 1 and Phase 2, including rate of durable transfusion independence, the 4- and 8-week mortality rates, the rate of subjects able to proceed to HSCT, and the MRD rate at the first response and at the best response. The time to event outcomes, including DOR, time to first response, time to best response, median duration to HSCT, EFS and OS, will be estimated using the Kaplan-Meier method. For the exploratory analysis, logistic regression models and Cox proportional hazards models will be fitted to correlate clinical factors, expressions of immune markers with efficacy outcomes. OS time will be calculated from the

date of the treatment start to the date of death or to the date of last follow-up if patients are alive at the time of data collection. Patients alive will be censored at the analysis. EFS will be calculated from the date of start treatment to the date of disease relapse or date of death whichever occurs first, or to the date of last follow-up for patients who are alive and have no relapsed disease at the time of data collection. Patients who are alive and have no relapsed disease will be censored at the analysis.

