**Table 2: Secondary Objectives and Their Endpoints and Category**

Secondary Objectives	Endpoints	Category
Phase 1 only: To evaluate the combined complete remission (CR) and CR with partial hematologic recovery (CRh) rate within 3 months of therapy initiation with DS-1594b in subjects with R/R AML or R/R ALL.	CR/CRh rate in Phase 1	Efficacy

Secondary Objectives	Endpoints	Category
Phases 1 and 2: To assess the composite CR (CRc) rate defined as CR + complete remission with incomplete blood count recovery (CRI), morphologic leukemia free survival (MLFS), partial remission (PR), and overall response rate of subjects with R/R AML and R/R ALL treated on single-agent or combinations of DS-1594b.	CRC rate MLFS rate PR rate ORR (CR + CRI + MLFS + PR) rate	Efficacy
Phases 1 and 2: To determine the: 

• duration of response (DOR),

• time to first response, time to best response,

• rate of durable transfusion independence (TI),

• event-free survival (EFS),

• overall survival (OS),

• measurable residual disease (MRD) by multiparameter flow cytometry at first response and best response,

• 4- and 8-week mortality, and

• number of subjects able to proceed to hematopoietic stem cell transplantation (HSCT) without additional AML therapy and median duration to HSCT from the initiation of single-agent or combinations of DS-1594b in subjects with RR AML and R/R ALL

	

• DOR,

• time to first response, time to best response,

• TI rate,

• EFS,

• OS,

• MRD rate by multiparameter flow cytometry at first response and best response,

• 4- and 8-week mortality

• number of subjects able to proceed to HSCT without additional AML therapy and median duration to HSCT from the initiation of single-agent or combinations of DS-1594b in subjects with R/R AML and R/R ALL

	Efficacy
Phases 1 and 2: To characterize single and multiple-dose pharmacokinetics (PK) of DS-1594b and its metabolites	Cmax, Ctrough, Tmax, Tlast, AUClast, AUCltau, AUCinf, Kel, t1/2, CL/F, Vz/F, AR	PK

Secondary Objectives	Endpoints	Category
Phase 1 only: In a subset of subjects, to evaluate the effect of multiple doses of antifungal agents that are strong CYP3A inhibitors on the PK of DS-1594b	Cmax, Ctrough, Tmax, Tlast, AUClast, AUCtau, AUCinf, Kel, t1/2, CL/F, Vz/F	PK

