## 2. BACKGROUND

### 2.1. Acute Myeloid Leukemia

Acute Myeloid Leukemia (AML) is a hematologic neoplasm characterized by the proliferation of poorly differentiated myeloid progenitor cells. The disease is particularly difficult to treat in older adults who account for the majority of subjects; thus, the 5-year overall survival is only approximately 27% in newly diagnosed AML. In recent years, multiple studies have characterized distinct molecular subgroups of AML, leading to the discovery of certain disease-associated mutations that are now being used to classify disease, dictate prognosis and, in some cases, guide therapy.

Approximately, 30 to 40% of adults with AML fail to achieve CR with 1 or 2 cycles of induction chemotherapy and are deemed primary refractory. The outcome of subjects with AML who are refractory to induction therapy are dismal, with low response rates (CR/CRi = 15 to 25%) to salvage chemotherapy and poor long-term survival, median OS 4-7 months. We have previously reported a dismal median OS of 3.8 months for subjects with AML who are refractory to HiDAC-containing induction therapy (defined as  $\geq 1\text{gm}/\text{m}^2$  cytarabine per dose). Salvage therapy in such subject populations yielded a response rate of 18% and median response duration of 9 months. These results emphasize the need to explore alternate salvage regimens for subjects with relapsed/refractory AML. The development of novel and effective anti-AML agents and/or combinations is crucial to improving the outcome of AML.

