## 9.4. Statistical Analysis Plan

### 9.4.1. Analysis Sets

#### 9.4.1.1. Efficacy Analysis Set

The efficacy analysis set is all subjects with MLLr or NPM1m who received at least one dose of DS-1594b. Each cohort will be analyzed separately for efficacy.

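### Kaplan-Meier is named for time to response and time to HSCT without a population or a rule for death; in all treated subjects it would bias the time curves upward and the medians downward

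*Combined protocol and SAP*

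**What the plan says.** Section 9.4.6 (Efficacy Analyses) lists DOR together with the endpoints at issue and assigns one method to all: "time to first response, time to best response, median duration to HSCT, EFS and OS, will be estimated using the Kaplan-Meier method". It then writes event and censoring rules for two of them only. OS runs from the "date of the treatment start to the date of death or to the date of last follow-up if patients are alive". For the other, "EFS will be calculated from the date of start treatment to the date of disease relapse or date of death whichever occurs first". Death is an event in both. Time to first response, time to best response and time to HSCT get no such rule. Section 9 names no competing-risk method.

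Table 2 lists the transplant endpoint as the "number of subjects able to proceed to HSCT without additional AML therapy and median duration to HSCT from the initiation of single-agent" or combination treatment. It gives no population for the median.

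Section 9.4.6 runs the efficacy analyses in the Efficacy Analysis Set and the Safety Analysis Set. Section 9.4.1.1 states: "The efficacy analysis set is all subjects with MLLr or NPM1m who received at least one dose of DS-1594b". Section 9.4.1.2 defines the safety set by receipt of one dose. Neither set is limited to responders or transplanted subjects.

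The proportions are handled separately. The primary response rate "will be estimated along with the 95% credible interval for each cohort", and the same method covers other binary outcomes, including "the rate of subjects able to proceed to HSCT, and the MRD rate at the first response and at the best response".

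**The concern.** A subject who dies before responding or being transplanted can no longer do either. Kaplan-Meier has only two states, event and censored, so in an all-treated set such a death becomes a censoring. The method then treats that subject as still able to have the event later, with the same chance as those who remain at risk. The complement of the curve no longer estimates the share of subjects who have had the event by a given time. It estimates a hypothetical share with death removed, which is higher.

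Death is not rare in this population. Section 2.1 describes refractory AML on salvage therapy with "median OS 4-7 months", and 3.8 months after induction containing high-dose cytarabine. Section 9.3 puts the historical response rate at 25% and the target at 40%, so more than half of the subjects are expected not to respond within 3 months.

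What is at stake is the time curves and their medians, above all the median duration to HSCT, which is a named secondary endpoint. Two analysts could follow the present text and report different numbers. One of them could report a curve that sits well above the HSCT proportion in the same report.

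**Working it through.** **The plan's own figure.** Section 9.4.6 gives no figure for the time analyses. Its one figure is the credible interval for 11 responders of 26. With the beta(0.5, 0.5) prior of Section 9.3 the posterior is Beta(0.5 + 11, 0.5 + 15) = Beta(11.5, 15.5). Its 2.5% and 97.5% quantiles are 25.0% and 61.3%, as stated. Deaths stay in the denominator of 26, so the issue does not touch this estimate.

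**Inputs from the documents.** Median OS of 3.8, 4 and 7 months (Section 2.1); response of 25% and 40% with a 3-month window (Sections 9.2 and 9.3); 26 subjects per cohort (Section 9.3).

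**Assumptions.** Constant hazards; the cited OS used as a proxy for death before the event; 12-month HSCT rates of 10%, 20% and 30%, since the documents give none; every death before the event censored.

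**Formulas.** Let d = ln 2 / (median OS) be the death hazard and r the event hazard.

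- True proportion by time t (cumulative incidence): r/(r + d) × [1 − exp(−(r + d)t)]
- Kaplan-Meier complement with death censored: 1 − exp(−rt)
- Long-run proportion with the event: r/(r + d)
- Kaplan-Meier median: ln 2 / r

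For each case r is solved so that the first formula gives the chosen true proportion.

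**One case in full.** Median OS 4 months gives d = 0.1733 per month. A true 40% response at 3 months needs r = 0.2298: 0.2298/0.4031 × [1 − exp(−0.4031 × 3)] = 0.40. The Kaplan-Meier complement is 1 − exp(−0.2298 × 3) = 49.8%. The excess is 9.8 points, or 13.0 implied responders of 26 against 10.4.

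**All cases: Kaplan-Meier complement**

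| Endpoint | True | OS 3.8 mo | OS 4 mo | OS 7 mo | Excess (points) |
|---|---|---|---|---|---|
| Response, 3 mo | 25% | 31.9% | 31.5% | 28.7% | 4 to 7 |
| Response, 3 mo | 40% | 50.3% | 49.8% | 45.6% | 6 to 10 |
| HSCT, 12 mo | 10% | 23.6% | 22.8% | 16.8% | 7 to 14 |
| HSCT, 12 mo | 20% | 44.7% | 43.5% | 32.9% | 13 to 25 |
| HSCT, 12 mo | 30% | 63.1% | 61.6% | 48.2% | 18 to 33 |

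**Medians.** At 40% response by 3 months the Kaplan-Meier median is 2.97, 3.02 and 3.42 months (OS 3.8, 4 and 7). The cumulative-incidence median is 5.33, 5.20 and 4.52 months.

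At 30% transplanted by 12 months the long-run proportion is 31% to 36%, so half of the subjects are never transplanted and no cumulative-incidence median exists. The model Kaplan-Meier median is nevertheless 8.3, 8.7 and 12.6 months.

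**Check at the planned size.** In 4,000 simulated cohorts of 26, with 24 months of follow-up and no transplant after month 12, the 30% case gave a finite Kaplan-Meier median in 72%, 69% and 42% of runs (OS 3.8, 4 and 7). At an assumed 20% the figures were 35%, 33% and 10%.

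**The case against.** The strongest reply is that the plan nowhere says deaths are censored. It leaves the rule unwritten, and listing the median time to HSCT beside the number transplanted could mean transplanted subjects only. On that reading nobody is censored, Kaplan-Meier reduces to the ordinary sample distribution and its median is the sample median. The method is then redundant but not biased. This stands as a possible reading. It does not close the point: the sets named for efficacy are all treated subjects, no restriction to subjects with the event is written, and a median in that subgroup must be labelled as conditional on the event.

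A reader might also infer that the trial will overstate how many subjects respond or reach transplant. The documents do not support that. Those counts and rates are binary outcomes with credible intervals, and deaths stay in their denominators. Nor do the documents support a flat statement that most subjects never reach transplant, since they give no HSCT rate.

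Two limits on the size also stand. The cited survival is for refractory AML, not for ALL (Cohort D) or for subjects treated to a 40% response target. And OS in all subjects is only a stand-in for death before the event.

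Finally, these are secondary, descriptive endpoints. That lowers the consequence but does not make a biased median informative.

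**Conclusion.** The point holds for the time curves and medians. The plan names a method for three endpoints without population, censoring rule or handling of death. Applied in the usual way to the sets it specifies, that method biases the curves upward and the medians downward. It can also return a median time to HSCT when fewer than half of the subjects are transplanted.

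The overstatement is about 4 to 10 points for response at 3 months, and about 7 to 33 points for HSCT at 12 months. Both ranges are conditional on deaths being censored in all treated subjects, on constant hazards and on the cited median OS. The HSCT range rests in addition on assumed rates of 10% to 30%. Censoring at death is inferred from standard use of Kaplan-Meier and is not stated in the plan. The response and HSCT proportions, the primary endpoint and the futility and toxicity boundaries do not change.

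**What to change.** In Section 9.4.6:

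- For time to first response, time to best response and time to HSCT, state the population (all treated subjects in the efficacy set), the start date, the event and the competing events.
- Estimate these by Aalen-Johansen cumulative incidence, with death without the event as a competing event. For HSCT also count additional AML therapy as competing, because Table 2 restricts the endpoint to transplant without it.
- Report the median duration to HSCT and the median times to response as simple median and range among subjects with the event, labelled as conditional on having it.
- Keep Kaplan-Meier for OS and EFS. Keep it for DOR with death stated as an event, since Section 9.4.6 gives DOR no rule either.

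The cost is a few sentences of SAP text and standard software. The change needs no larger sample and leaves the binary estimates as they are.

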**Partial remission (PR)**

- Neutrophil count:  $>1.0 \times 10^9/L$
- Platelet count  $>100 \times 10^9/L$
- $\geq 50\%$  reduction in bone marrow blast from pretreatment baseline, but still  $\geq 5\%$

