#### **8.8.4. Relapse Definition (AML and ALL)**

Hematological relapse is defined as marrow blasts  $\geq 5\%$  by morphology, persistent reappearance of blasts in the peripheral blood by morphology, or the occurrence of extramedullary disease after achieving remission (CR, CRh, CRI, or MLFS).

When relapse is suspected on the basis of the follow-up physical examination or peripheral blood counts, additional testing may be performed to confirm the finding, but the date of relapse is set to the date of the first test that suggests relapse.

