##### **Criteria for Protocol-Defined Required Discontinuation of Treatment**

The protocol requires discontinuation of study treatment for the following reasons:

- Lack of clinical benefit (defined as failure to achieve a PR or  $\geq 50\%$  reduction in bone marrow blast from pretreatment baseline within 6 cycles of treatment)
- Subject requests discontinuation.
- Unacceptable toxicity that in the opinion of the investigator makes it unsafe to continue therapy.
- Clinically significant progressive disease.

- Investigator discretion.

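### EFS counts only relapse or death, and relapse requires a prior remission, so for a subject who never remits EFS is the same as OS

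*Combined protocol and SAP*

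**What the plan says.** EFS is a named secondary endpoint for both phases (Section 1, Table 2), to be estimated by Kaplan-Meier. Section 9.4.6 defines it: "EFS will be calculated from the date of start treatment to the date of disease relapse or date of death whichever occurs first". For everyone else, "Patients who are alive and have no relapsed disease will be censored at the analysis", with time running to last follow-up. In the same section OS runs from the "date of the treatment start to the date of death or to the date of last follow-up".

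Section 8.8.4, which covers AML and ALL, lists three forms of relapse: marrow blasts of 5% or more, persistent reappearance of blasts in blood, "or the occurrence of extramedullary disease after achieving remission (CR, CRh, CRI, or MLFS"). PR is not on that list. Section 8.8.1 defines PR as at least a 50% "reduction in bone marrow blast from pretreatment baseline, but still" at 5% or above.

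Treatment failure appears only as a reason for stopping treatment. Section 8.9.1 requires discontinuation for "Lack of clinical benefit (defined as failure to achieve a PR or" at least a 50% marrow blast reduction within six cycles), and for "Clinically significant progressive disease". Sections 6.9 and 8.3 also refer to progression. None of these makes it an EFS event, and Section 8.8 gives no criteria for progressive disease.

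**The concern.** An event-free survival curve is expected to register the point at which treatment stops working. As written, it can do so only for subjects who first remit. A non-remitter who progresses, comes off study drug and lives on later therapy counts as event-free until death or last follow-up. For that subject EFS carries no information beyond OS.

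The direction is fixed. Adding an event type can only shorten or leave unchanged each subject's EFS time, so EFS as written is equal to or longer than an EFS that counts failure. A reader who assumes that failure is counted would take too favourable a view of a drug tested in relapsed or refractory disease, where non-remission may be the commonest outcome.

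**Working it through.** The plan states no EFS estimate, event count or power, so there is no figure to reproduce. The main check is logical.

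**Identity.** For a subject who never reaches CR, CRh, CRi or MLFS, no relapse date exists. Then EFS = min(relapse, death) = death or, if alive, last follow-up. OS has the same start, the same event and the same censoring date, so time and status coincide.

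**Alternative reading.** The prior-remission condition could be attached grammatically to extramedullary disease alone. Marrow blasts of 5% or more would then be relapse in their own right. A PR subject, who by definition still has 5% or more, would count as relapsed, as would most subjects at baseline. That reading is untenable, so the condition must govern all three forms.

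**How many subjects.** Section 9.3 gives response rates of 25% (historical) and 40% (target), with 26 subjects per cohort:
- 26 × (1 − 0.25) = 19.5
- 26 × (1 − 0.40) = 15.6

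At those rates, about 16-20 is an upper bound. The rates refer to CR+CRh (CR+CRi in Cohort D) within three months, whereas the Section 8.8.4 list is wider and has no time limit. The number could be larger if response falls below 25%.

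**Illustration of size.** Section 2.1 gives one group with every input documented, AML refractory to high-dose cytarabine induction: response 18%, median OS 3.8 months, median response duration 9 months. Assumptions, not from the documents: remitters are event-free to 1.5 months and then exponential with a 9-month median; non-remitter survival is exponential, with its hazard solved so that the mixture has median OS 3.8 months. Two bounds on remitter survival:
- All remitters alive at 3.8 months: non-remitter survival at 3.8 months = (0.5 − 0.18)/0.82 = 0.390. Hazard = −ln(0.390)/3.8 = 0.248 per month, median 2.80 months, six-month survival 0.226.
- Remitter survival equal to remission duration: exp(−ln 2 × 2.3/9) = 0.838. Non-remitter survival at 3.8 months = (0.5 − 0.18 × 0.838)/0.82 = 0.426. Hazard 0.225, median 3.09 months, six-month survival 0.260.

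If every remission precedes any failure date, and every never-remitter alive at six months has failed by then, the six-month gap = (1 − share remitting) × non-remitter six-month survival:
- 25% remitting: 0.75 × 0.226 to 0.75 × 0.260 = 17.0 to 19.5 points
- 40% remitting: 0.60 × 0.226 to 0.60 × 0.260 = 13.6 to 15.6 points

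**Median EFS if failure is dated only at the end of Cycle 6.** Day 168 is 168/30.44 = 5.52 months, when non-remitter survival is 0.255-0.289. Remitters still event-free then: exp(−ln 2 × 4.02/9) = 0.734. The proportion event-free just before day 168 is:
- 25% remitting: 0.25 × 0.734 + 0.75 × (0.255 to 0.289) = 0.37 to 0.40
- 40% remitting: 0.40 × 0.734 + 0.60 × (0.255 to 0.289) = 0.45 to 0.47

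Both are below one half, so the median falls before day 168, where the two curves are identical: 3.8-4.1 and 4.7-5.0 months under either definition. The share of subjects whose EFS time changes is 0.75 × (0.255 to 0.289) = 19-22%, or 0.60 × (0.255 to 0.289) = 15-17%.

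**Where the median does move.** The other group in Section 2.1 (induction-refractory AML) has 15-25% response and median OS 4-7 months. Its response duration is not given; I assumed 6-12 months. Under the same model and dating, with 4-month OS the median is unchanged at 25% remission and moves by at most 0.13 months at 40%. With 7-month OS it falls by up to 2.0 months at 25% and 3.0 months at 40%.

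**The case against.** The definition is explicit and can be analysed as it stands, and no section says that EFS must include treatment failure. EFS is one of many descriptive secondary endpoints with no threshold or decision attached. Response, DOR, OS and discontinuation reasons are all reported separately. All of this stands, and it limits the weight of the point. It does not remove the redundancy with OS or the censoring of progressed subjects as event-free.

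The six-month reading is also unflattering to the plan, because it falls just after day 168. That is fair, and the unchanged median is part of the result.

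A reader might infer that EFS is wrong for the 60-75% who would not respond at the plan's rates. The documents do not support that: the remission list is wider than the response endpoint, and a non-remitter who dies before any failure date has the same EFS under either definition. A reader might also carry the illustration over to the other Section 2.1 group and quote a gap of up to about 41 points. That figure needs an assumed response duration, and it applies survival solved at 15% response to a 25% remission rate.

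**Conclusion.** The point holds as a matter of definition: for any subject without CR, CRh, CRi or MLFS, EFS repeats OS, and failure while alive is not registered. It rests on last follow-up being the same date for EFS and OS; the text uses the same term for both.

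At most about 16-20 of 26 subjects per cohort are concerned at 25-40% response. The numerical gap cannot be derived from the documents. The 14-20 points at six months is an illustration from one refractory-AML group, not selected for MLLr or NPM1m, and says nothing direct about ALL or the combination cohorts. It should not be read as an inflated median: in that group the median does not move under Cycle 6 dating. It shifts only where OS is longer or where progression or stopping is dated earlier, and the documents give no rate for the latter.

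Nor should it be read as a threat to the trial's main conclusions. The primary endpoint, the futility and toxicity monitoring and the sample size do not use EFS.

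**What to change.** Amend Section 9.4.6. This is an analysis change only; no treatment rule is touched.

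- Define the EFS event as the earliest of treatment failure, relapse after remission, or death.
- Define treatment failure, in a subject without prior remission, as progressive disease, stopping treatment for progressive disease or lack of benefit, or no remission by the end-of-Cycle-6 assessment. Use the Section 8.8.4 list (CR, CRh, CRi or MLFS) for both diseases, so that nobody is both a failure and eligible to relapse.
- Date failure at documented progression or stopping, otherwise at the Cycle 6 assessment. Use the progression and discontinuation dates already recorded.
- State that the Cycle 6 criterion is an EFS convention stricter than Section 8.9.1, which accepts PR or a 50% blast reduction.
- State how non-remitters are handled who stop for other reasons (for example "Unacceptable toxicity that in the opinion of the investigator makes it unsafe to continue therapy"), start new anti-leukaemic therapy, or go to HSCT.
- Keep the present definition as a supportive analysis labelled *relapse or death only*.

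The cost is a short protocol amendment, because the SAP is Section 9.4 of the protocol, and a less favourable reported EFS. The Cycle 6 marrow and the follow-up of subsequent therapy are already scheduled, and reasons for discontinuation are already summarised.
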